7.3. Adjustment of P values for Multiple Testing

There is no multiple testing as only a single primary outcome is considered. All additional analyses are undertaken with an intention to further inform the results from the primary analysis. Therefore significance levels used will be 0.05 and 95% confidence intervals will be reported.

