10.3. Interim analyses

Four interim analyses will be performed on the primary endpoint whenever 25% of patients has been randomised and have completed the 60 (± 5) days follow-up. The interim analyses will be performed by a trial statistician in coordination with the study team. The statistician will report to the independent data and Data and Safety Monitoring Committee (DSMC). The DSMC will have unblinded access to all data and will discuss the results of the interim-analysis during a DSMC meeting. A trial steering committee will also be constituted and will decide on the continuation of the trial and will report to the central ethics committee. The trial will be terminated if superiority of either short or long treatment durations is shown. We will use the group sequential design adopting the boundaries proposed by Fleming- Harrington- O'Brien ($R=0.8$) [41] to terminate the trial prematurely once the Z value exceeds the defined boundaries for superiority.

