2.2. Study Design

The study design is a randomised, partially double-blinded (blinding may be achieved up to 7 days) controlled trial to assess the efficacy of short versus longer antibiotics course in adults with VAP. The trial has a stepwise noninferiority–superiority hypothesis, i.e. if non-inferiority of short duration, compared with long duration, is shown, statistical tests for superiority will be performed using closed testing methods without requiring adjustment of the significance level for multiple comparisons.

Period of external pilot	19 February 2018 to 23 May 2018
Date of start of recruitment	25 May 2018
Date of end of recruitment	16 December 2022
Date of end of follow-up	14 February 2023
Date of expected analysis	14 March 2023 to 14 May 2023
target number of participants	460 (230 per arm)

Participating study sites include:

- 1) National University Hospital, Singapore
- 2) Tan Tock Seng Hospital, Singapore
- 3) Sunpasitthiprasong Hospital, Ubon Ratchathani, Thailand
- 4) Srinagarind Hospital, Khon Kaen, Thailand
- 5) Patan Academy of Health Science, Patan Hospital, Kathmandu, Nepal
- 6) Civil Hospital, Kathmandu, Nepal
- 7) Khon Kaen Hospital, Khon Kaen, Thailand
- 8) Cajuru University Hospital, Pontifical Catholic University of Paraná, Brazil

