2.6. Hypotheses and Definition of Primary and Secondary Outcomes

Primary end point

The primary end point of the study is the difference in the proportion of participants with the composite endpoint of death and VAP recurrence rate within 60(± 5) days of enrolment.

Death refers to all-cause mortality. VAP recurrences are episodes which satisfy the US CDC VAP criteria, and verified by two independent respiratory or infectious diseases physicians blinded to the randomisation arm.

The first statistical test for the primary end point will be for non-inferiority. Here, the null hypothesis (H_0): $\theta \geq \delta$ will be tested against the alternative (H_1): $\theta < \delta$, where θ is the treatment effect difference between the proportion of participants who have the primary outcome in the short and long treatment strategy groups, and δ is the fixed non-inferiority margin of 12%.

In the event that short is non-inferior to the long treatment strategy, standard two-sided superiority testing will be performed. That is, the null hypothesis (H_0): $\theta = 0$ will be tested against the alternative (H_1): $\theta > 0$, where θ is the treatment effect difference between the proportion of participants who have the primary outcome in the short and long treatment strategy groups.

Secondary end points

All statistical tests for the secondary endpoints are standard two-sided superiority tests.

a) Ventilator-associated events

Definition: Events which satisfy the US CDC VAP criteria ¹ but were not verified by two independent respiratory or infectious diseases physicians.

H_0 : There is no difference in the proportion of participants who have ventilator-associated events in the short and long treatment strategy groups, i.e. $\theta^{VAE} = 0$;

H_1 : There is a difference in the proportion of participants who have ventilator-associated events in the short and long treatment strategy groups, i.e. $\theta^{VAE} \neq 0$;

where θ^{VAE} is the treatment effect difference between the proportion of participants in the short and long treatment strategy groups.

b) Duration of mechanical ventilation

Definition: Total duration of mechanical ventilation during the 60 days of follow-up after enrolment.

H_0 : There is no difference in the total duration of mechanical ventilation in the short and long treatment strategy groups, i.e. $t^v_s = t^v_l$;

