4. DATA SAFETY MONITORING COMMITTEE AND INTERIM ANALYSES

The data safety and monitoring committee (DSMB) consists of members independent from the study investigator team. The DSMB will review the analysis plan, interim analyses results, and their approval will be required before protocol and analysis plan amendments. The DSMB will receive reports regarding severe adverse events on a monthly basis, and will review the final study report. The DSMB will be empowered to advise stopping or suspending the trial, independent of the study investigators.

DSMB meetings should be held with every interim analysis and extra meetings may be convened at the request of the investigators, sponsor, or DSMB members to discuss emerging data that is a cause for concern. A full interim analysis including all available data from all sites will be reviewed by the DSMB after approximately 25% (125) participants from sites have been recruited and completed their follow-up to review the safety and ethics of the REGARD-VAP trial. Hence there will be four interim analyses will be performed on the primary endpoint.

A trial steering committee will also be constituted and will decide on the continuation of the trial and will report to the central ethics committee. The trial will be terminated if superiority of either short or long treatment durations is shown. We will use the group sequential design adopting the boundaries proposed by Fleming- Harrington- O'Brien ($R=0.8$)⁵ to terminate the trial prematurely once the Z value exceeds the defined boundaries for superiority.

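### SAP 7.3 denies any multiple testing and keeps 0.05 although superiority is also tested at interim looks, and SAP 4's look size of 125 does not fit 460 patients, so the final critical value is unsettled (minor)

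*SAP*

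**What the plan says.** SAP 7.3 (Adjustment of P values for Multiple Testing) says "There is no multiple testing as only a single primary outcome is considered" and concludes that "significance levels used will be 0.05 and 95% confidence intervals will be reported". SAP 2.6 says that, once non-inferiority is shown, "standard two-sided superiority testing will be performed". SAP 2.2 adds that "statistical tests for superiority will be performed using closed testing methods without requiring adjustment of the significance level for multiple comparisons"; Protocol sections 5 and 10.1 say the same.

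SAP 4 places a full interim review "after approximately 25% (125) participants from sites have been recruited and completed their follow-up" and infers from this: "Hence there will be four interim analyses will be performed on the primary endpoint". Protocol 10.3 (Interim analyses) reads: "Four interim analyses will be performed on the primary endpoint whenever 25% of patients has been randomised", with 60-day follow-up complete. Both documents end the trial if either duration proves superior. Both use Fleming-Harrington-O'Brien boundaries with R=0.8 "to terminate the trial prematurely once the Z value exceeds the defined boundaries for superiority".

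Neither document lists a Z value or a final-look critical value, and SAP 7.3 does not refer to SAP 4. The sample size text (SAP 2.5; Protocol 10.2, The Number of Participants) gives at most 412 evaluable and 460 enrolled patients. The only alpha it attaches to the group sequential design is one-sided 5%, for non-inferiority.

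**The concern.** The reason given in SAP 7.3 does not support its conclusion. A single outcome removes multiplicity across outcomes. It does not remove the multiplicity of testing that outcome several times with the option to stop and claim superiority. The closed-testing statement does not fill the gap, because it covers only the step from non-inferiority to superiority at one analysis.

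The look schedule makes this harder to resolve. If the fourth look is the final analysis, SAP 4's boundary and the ordinary two-sided 0.05 test of SAP 2.6 and 7.3 are competing rules for the same test. If it is not, the final test comes on top of four looks. In either case a reader cannot tell which critical value or confidence level a superiority claim must meet. What is at stake is the clarity of that claim and a slight excess of false superiority. The non-inferiority conclusion is not at stake, provided the boundaries stop for superiority only.

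**Working it through.** **1. Look size.** Inputs: 460 enrolled and 412 evaluable (SAP 2.5); about 25%, given as 125 (SAP 4).
- 0.25 × 460 = 115 and 0.25 × 412 = 103. Neither gives 125.
- 125/460 = 27.2%; 125/0.25 = 500.
- Four steps: 4 × 125 = 500, above the maximum of 460.
- True 25% steps: 115, 230, 345, 460 enrolled, or 103, 206, 309, 412 with completed follow-up. The fourth is the whole sample.

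**2. Two-sided superiority error with the final test at 1.96.** The documents neither list the boundaries nor explain R=0.8. I therefore assumed three families, each built for an overall two-sided 0.05: (A) O'Brien-Fleming type; (B) 80% of alpha kept for the final look, the rest spread equally over the interims; (C) final look at nominal 0.8 × 0.05 = 0.04, with equal interim spending. The final boundary was then replaced by 1.96 and the error computed under no true difference by numerical recursion:

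| Looks | A | B | C |
|---|---|---|---|
| 115/230/345/460 | 5.62% | 5.37% | 5.91% |
| 125/250/375/460 | 5.69% | 5.33% | 5.90% |
| four equal interims plus a final | 5.73% | 5.36% | 5.91% |

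Without the non-inferiority gate the range is 5.3-5.9%. The final-look Z values that would hold 5% are 1.99 to 2.05.

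**3. Adding the gate.** SE of the difference at 460 patients and 55% in both arms: √(4 × 0.55 × 0.45/460) = 4.64 points. A final result at Z = 1.96 against the short arm is 1.96 × 4.64 = 9.1 points. Its upper 90% limit is 9.1 + 1.645 × 4.64 = 16.7, above the 12-point margin, so the gate blocks it. A final result of 9.1 points in favour of short always passes. Long can therefore be declared superior only at an interim look. The total is half the ungated error (short superior) plus the interim probability for long. For 25% steps:
- A: 5.62/2 + 1.05 = 3.9%
- B: 5.37/2 + 0.50 = 3.2%
- C: 5.91/2 + 1.02 = 4.0%

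Over all three schedules the range is 3.2-4.2%. The top value is family A with looks at 125: 5.69/2 + 1.31 = 4.2%.

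**4. False short-superior rate (nominal 2.5%).** Half the ungated totals: 2.7-3.0%. Protocol 10.1 requires the confidence intervals of all the trial estimates to agree before superiority is declared; the SAP does not repeat this. I read that rule in the direction favouring short. The simulation used 16 million paths and 25% steps, with interims on the intention-to-treat (ITT) population. The per-protocol (PP) population was assumed to be a random subset of ITT, with correlation √adherence, and both had to pass 1.96 at the end:

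| Adherence | A | B | C |
|---|---|---|---|
| 100% | 2.81% | 2.68% | 2.95% |
| 98% | 2.52% | 2.37% | 2.66% |
| 95% | 2.37% | 2.19% | 2.49% |
| 80% | 1.98% | 1.71% | 2.07% |

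By 95% adherence the excess is gone in all three families.

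**The case against.** The best defence is that SAP 7.3 concerns multiplicity of outcomes only. Its 0.05 cannot be a universal level, because SAP 7.2 uses a two-sided 90% interval for non-inferiority. If it does not override 7.2, it need not override SAP 4, which names a group sequential design with a cited source. Read that way, two-sided 0.05 is the overall superiority level, the named design controls error at 5%, and only a cross-reference, the Z values and the look counts are missing. The count is hedged as approximate, 125 is 27% of 460, and the exact schedule barely moves the error rate (5.62% against 5.69% in family A). The agreement rule also spans adjusted and unadjusted estimates in both populations, so modelling two estimates overstates the excess. Adding the adjusted estimates at an assumed correlation of 0.98 (family A) gives 2.4% at full adherence.

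Much of this stands. It is why the point is minor, and why two-sided 0.05 is the natural overall level to write down. It does not rescue the text. SAP 7.3 gives a wrong reason, SAP 2.6 calls the final test standard, and nothing tells the analyst to use a final-look boundary. The word approximately can cover one look at 27%, but not four such steps within 460.

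Three stronger readings are tempting, and the documents do not support them. First, the looks are not uncorrected: 12.6% (four looks) or 14.2% (five) would apply only if every look used 1.96, and both documents name boundaries. Second, boundaries built for two-sided 0.10 would give 5.8-7.9% without the gate, but no section describes them; the one-sided 5% in the sample size text is for non-inferiority. Third, the non-inferiority test is not shown to be inflated, because the stated stopping rule is for superiority.

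**Conclusion.** The text defects are real and the point is minor. SAP 7.3 is wrong to say that there is no multiple testing. The figure of 125 is not 25% of either planned total. The plan does not settle which critical value governs the final superiority test.

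The numerical consequence is small and conditional. The 5.3-5.9% figure leaves out a gate that the plan does contain. With the gate, total error stays below 5%. What remains is a false short-superior rate at most about 0.5 points above nominal, and none if Protocol 10.1's agreement rule applies and adherence is about 95% or lower. These rates rest on assumed boundary shapes built for two-sided 0.05, a final test at 1.96, and PP as a random subset of ITT. The textual and count findings rest on none of these. The statement that non-inferiority is unaffected depends on the boundaries stopping for superiority only. The plan should confirm this, because the sample size text also ties the group sequential design to non-inferiority.

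**What to change.** 1. **SAP 7.3 and 2.6.** Replace the first sentence of 7.3 with a statement that the primary endpoint is also tested for superiority at the section 4 looks; that two-sided 0.05 is the overall superiority level; and that the final superiority test and its confidence interval use the final-look critical value of the Fleming-Harrington-O'Brien (R=0.8) design for the looks actually held. Make 2.6 refer to that value. Another overall level should be accepted only if it was documented before the first look: follow-up ended on 14 February 2023 (SAP 2.2) and the statistician is not blinded (SAP 9.2), so an open choice now would be post hoc.
2. **SAP 4 and Protocol 10.3 (Interim analyses).** Correct 125 in SAP 4. In both documents, give look counts that fit the sample (115/230/345/460 enrolled, or 103/206/309/412 with completed follow-up), or the looks actually held according to the monitoring committee's records. Say whether the fourth look is the final analysis, list the Z boundaries used, and say that they govern superiority only, if that is so.

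The cost is a few sentences, a short table and a check of the committee's records. The downside is a slightly stricter final superiority threshold. At 460 patients and 55% in both arms, it moves from 9.1 points to about 1.99 × 4.64 = 9.2 up to 2.054 × 4.64 = 9.5 points under the assumed boundaries.

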7.4. Missing Data

Minimal amounts of missing data are expected in the REGARD-VAP study as most information could be retrieved from the medical notes and frequent follow-ups from the research teams. Loss to follow-up may arise primarily in cases where participants formally withdraw from all further follow-up or relocate or their medical records can no longer be accessed. Low percentages of missing data are not expected to have a significant impact on the trial results, and therefore no sensitivity analysis to examine the impact of missing data is planned if complete outcome data is available for more than 95% of participants (i.e. less than 5% of participants are lost or withdraw from follow-up before 60 days).

However, in the event that the extent of missing data will exceed this level, multiple imputation models will be used to adjust for missing data. Data will be imputed based on the covariates used in the multivariable models (allowing for a possible non-linear effect of age), the log(last follow-up time) and a treatment failure indicator which will be set to missing for those with incomplete follow-up due to loss / withdrawal. Twenty imputed datasets will be created, and results will be pooled using the standard methodology (Rubin's rule) and 'mice' package in R¹⁰. Visual checks to compare the distribution of observed and imputed values will be performed to ensure the imputation model includes non-linear effects of continuous variables where appropriate. Multiple imputation assumes that the missing data follows a missing at random mechanism, i.e. the probability of an observation being missing can be explained by the observed data. Under this assumption, an imputation model that includes the appropriate variables will produce unbiased results. A secondary sensitivity analysis to assess the potential impact of missing data will also include a data missing not at random scenario, assuming that participants with missing data have worse outcomes than those with complete follow-up data, following the approach by White *et al*¹¹.

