7.1. Evaluation/Definition of Primary Outcome

The primary endpoint of the REGARD-VAP trial will be analysed as a binary outcome (i.e. not as a time to event outcome) because dates may reflect timing of observations rather than actual failure. In this analysis, any participant with incomplete follow-up and no event observed to date will be classed as not having experienced an endpoint.

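### SAP 7.4 imputes the missing primary outcome from log(last follow-up time); if follow-up ends at death, most participants lost alive would be imputed as failures

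*SAP*

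**What the plan says.** The primary endpoint is death or verified VAP recurrence within 60 (±5) days of enrolment, and "Death refers to all-cause mortality" (SAP 2.6). For the primary analysis, SAP 7.1 states that "any participant with incomplete follow-up and no event observed to date will be classed as not having experienced an endpoint".

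SAP 7.4 then sets out the handling of missing data. It says that "no sensitivity analysis to examine the impact of missing data is planned if complete outcome data is available for more than 95% of participants". Otherwise the outcome is imputed from the covariates of the multivariable models, together with "the log(last follow-up time) and a treatment failure indicator which will be set to missing for those with incomplete follow-up" due to loss or withdrawal. "Twenty imputed datasets will be created" and pooled by Rubin's rule with the R package mice. Under missing at random, the section says, "an imputation model that includes the appropriate variables will produce unbiased results". Visual checks of observed against imputed values are meant "to ensure the imputation model includes non-linear effects of continuous variables where appropriate". A further missing-not-at-random scenario is planned, "assuming that participants with missing data have worse outcomes than those with complete follow-up data". SAP 7.7 adds no other sensitivity analysis.

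Neither document says what last follow-up time means for a participant who died.

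**The concern.** An imputation model learns from participants whose outcome is known. Here, a known outcome with short follow-up arises in essentially one way. Survivors complete at the day 60 (±5) visit (protocol section 5, Follow-up visits), so anyone with a complete record that stops well before day 55 has died, and death is a failure. A participant who withdraws alive and event-free on day 20 would be compared, at that follow-up time, only with people who died around day 20.

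At stake is the meaning of the one analysis that the SAP labels missing-at-random. It should be the realistic middle estimate, because the primary rule counts lost, event-free participants as non-failures and the remaining scenario assumes worse outcomes. If it instead codes most of the lost as failures, a reader would take a near-extreme assumption for the neutral one.

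A second matter sits in the same sentence. The indicator is set to missing for everyone with incomplete follow-up, with no exception for a recurrence already verified. SAP 7.1 reclassifies only participants with no observed event, so it keeps that recurrence.

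**Working it through.** **1. The plan's own figures.** The documents give no figure for the imputation itself. The loss allowance reproduces: 412 / (1 − 0.10) = 457.8, planned as 460. The trigger is 0.05 × 460 = 23 participants and the allowance is 0.10 × 460 = 46. At the loss allowed for, the imputation would run.

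**2. Who informs the model at each follow-up length.** Assume that follow-up for a death ends on the death date.

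| Participant | Last follow-up | Failure indicator |
|---|---|---|
| Alive at day 60 visit, no recurrence | 55-65 days | 0 |
| Alive at day 60 visit, recurrence | 55-65 days | 1 |
| Died on day t | t | 1 |
| Lost alive on day t | t | missing |

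For t below 55, P(failure | follow-up = t, outcome known) = 1. Missing at random given follow-up time would require P(failure | follow-up = t, lost) to be 1 as well. That is false even when loss has nothing to do with prognosis. Including the term makes the stated assumption fail.

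**3. Simulation.**
- *From the documents:* 460 participants, 1:1, 55% composite rate, survivors seen at day 60 (±5), 20 imputations.
- *Assumed:* mortality 35% (range 20% to 42.8%, the latter being the top of the range in SAP 2.5) with recurrence making up the rest; exponential death times with mean 18 days, truncated at day 60; recurrences on days 5-45; one severity covariate; loss unrelated to prognosis.
- *Imputation:* logistic, on arm, severity and log time, with parameter draws and a guard against perfect prediction; 200 replicates.

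Every complete case with follow-up under 55 days was a failure.

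| Loss on days | Imputed failures, 35% mortality | True | Imputed, 20-42.8% mortality | True |
|---|---|---|---|---|
| 1-30 | 99% | 44% | 98-99% | 41-50% |
| 7-55 | 86% | 38% | 85-86% | 32-46% |
| 28-55 | 74% | 34% | 72-76% | 25-45% |
| 45-55 | 56% | 33% | 50-63% | 24-45% |

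Further runs with losses on days 8-50 gave 89-90% against 39-40%, and one for days 28-55 gave 73%.

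By day of last contact, at 35% mortality:

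| Day | Fitted failure probability | True risk if alive and recurrence-free |
|---|---|---|
| 7 | 1.00 | 0.49 |
| 14 | 0.999 | 0.40 |
| 28 | 0.97 | 0.24 |
| 42 | 0.77 | 0.07 |
| 50 | 0.57 | 0.02 |

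**4. Effect on the results** (losses on days 7-55 unless stated).
- *Event rate:* inflation = loss × (imputed − true share) = 0.090 × (0.858 − 0.385) = 0.043. This matches the simulated rise from 54.6% to 58.9%.
- *Risk difference, no true effect:* shift ≈ gap in realised loss × (imputed − true share). For nominal 15% v 5%, realised loss averaged 9% against a nominal 10%, so the gap is about 9 points and 0.09 × (0.860 − 0.369) = 0.044. Simulated: +4.3 points if the short arm loses more, −4.4 if the long arm does.
- *Other splits (days 8-50):* nominal 12% v 6% gave +2.2 or −2.2, and 15% v 7% gave +3.0. Realised gaps are smaller than nominal because some participants die before they would have been lost.
- *Equal loss:* no shift.

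For scale only: at 55% in both arms, the largest observed difference that passes the 12-point margin is 12 − 1.645 × √(2 × 0.55 × 0.45 / n) × 100, which is 3.9 points at n = 206 per arm and 4.4 at n = 230.

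**5. Recurrence before loss.** Between about 12% and 19% of the lost already had a recurrence in these simulations, depending on the assumed timing. Read literally, SAP 7.4 sets these to missing.

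**6. Is dropping the term enough?** Without it, the imputed share is 55%, and the 15% v 5% shift is still +1.7. If observed recurrences are also kept, the share is about 0.19 + 0.81 × 0.55 = 0.64; direct simulation gave 0.65, against a true 0.39. The reason is that the model still gives people known to be event-free at loss the whole-period risk.

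**The case against.** The strongest reply is that the result rests on a coding that the SAP does not state. If deaths were given full 60-day follow-up, the imputed share would be only 47-52%. This stands: the documents support a conditional statement, not the claim that every complete case with short follow-up must be a death. But no such rule is written, and ending follow-up at death is the natural reading.

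Other replies also have force.
- The imputation is a conditional sensitivity analysis. SAP 7.4 expects little missing data, and the 10% is an upper allowance used to size the trial.
- The unequal loss rates are assumptions found in neither document. If the short arm loses more, the shift works against non-inferiority; only the opposite split favours it.
- The share depends on when losses occur. It is near 100% for early losses, but 50-63% for losses confined to days 45-55. SAP 2.7 plans weekly mortality checks to day 60, which may make early loss uncommon.
- On recurrences, SAP 7.1 can be read as settling that observed events stand. Clarification is needed; deletion is not proven.

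The planned safeguards help less than they seem to. The visual check might expose an imputed share near 90%, but it is aimed at functional form, and a non-linear time term raised the share from 86% to 98%. Predictive mean matching gave 84%. The guard against perfect prediction was already in the model.

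A reader might also infer that the imputation duplicates the worse-outcome scenario. The documents do not show that, because SAP 7.4 does not say how much worse those outcomes are taken to be.

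**Conclusion.** The point holds in conditional form. If last follow-up time for deaths is the death date, the term makes the imputation treat most participants lost alive as failures: about 85-90% for losses spread over days 7-55 and about 73% for days 28-55, against a true 33-40%, assuming 35% mortality and loss unrelated to prognosis. At about 9% loss, the overall event rate rises by about 4 points. The risk difference moves only if loss differs by arm, by about 2-4 points over the splits examined.

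A reader might infer that the non-inferiority conclusion itself is at risk. The documents do not support that. The decision is taken under SAP 7.1 and 7.2, where lost, event-free participants count as non-events, and the imputation does not enter it. The 3.9-4.4 point figure describes that unadjusted primary comparison and serves here only to judge size.

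This is a should-fix point: a stated rule gives a misleading supporting analysis and is cheap to correct.

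**What to change.** Amend SAP 7.4 as follows.

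1. Remove log(last follow-up time) from the imputation model.
2. State that a death or verified recurrence observed before loss stays a failure, in line with SAP 7.1. Set the indicator to missing only for participants alive and event-free at last contact, and define the last-contact date.
3. Impute their day-60 outcome from participants still alive and event-free at the same time point, weekly or coarser, using the listed covariates. A discrete-time hazard model by interval does this.

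Step 1 alone, or steps 1 and 2 without step 3, would still overstate failures among the lost (working, step 6).

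The cost is SAP wording and modest programming. There is a small downside. SAP 7.1 warns that dates may reflect when an event was observed, and SAP 2.7 schedules recurrence screening only to discharge, although mortality is assessed weekly to day 60. The intervals should therefore be coarse, for example split at the day 28 visit after discharge, and the report should state this limit.
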